**NCT02063984 Unique Protocol ID: DA015186-DartmouthSpectrum**  
**Secondary IDs: R01DA015186-12A1**  
**Brief Title: Behavioral Treatment of Adolescent Substance Use (SMART)**

**2/17/15**

**Design, procedures, materials and methods:**

We will recruit adolescent male and females, who enroll in substance use treatment at Mountain Manor Treatment Center. Treatment is 26 weeks in duration total, and half the participants will be randomly assigned to Treatment A and receive CM/WMT and the other half of participants will be randomly assigned to Treatment B and receive CM only. Weeks 1-14 involve once weekly sessions with a therapist. The individual sessions will involve a review of substance use, the incentive program, spending ideas, and clarify any questions. The individual sessions will last approximately 30 minutes. Weeks 1-14 also involve once-weekly drug testing. In Treatment A, WMT will be delivered, usually starting in week 2 at Mountain Manor. Weeks 15-26 involve drug testing only. Post-treatment assessment will occur at the end of treatment. There will be three follow up assessments: 14 weeks, 6 months, and 12 months after intake. The final study visit will be the 12 month follow up assessment.

Participants will be randomly assigned to one of two first-line interventions (CM or CM with active WMT). Then treatment response will be assessed at week 4, and non-responders will be randomly assigned to either continue with assigned intervention or to an intensive contingency management (ICM) intervention.

**Clinical Site and Participant Recruitment:** Participants will present for treatment at Mountain Manor Treatment Center in Baltimore, Maryland. Counselors are Master's level licensed Psychology Associates.

Youth who present for substance use treatment at Mountain Manor will be screened for eligibility and provided the opportunity to participate in the study. We expect to enroll at least 5 youth per month based on the census at Mountain Manor and their history of recruiting youth in their programs into clinical research protocols.

**Treatment Components Delivered to all Participants**

**Clinic-delivered CM.** All youth will receive our standard escalating CM incentive program. In weeks 1-2, participants receive \$10 incentives for each urine specimen provided as scheduled, regardless of results to facilitate initial compliance with providing specimens. During weeks 3-14, the program targets abstinence from marijuana and other substances by awarding incentives for documented abstinence. Abstinence is defined as abstinence from all substances determined by: 1) urine and breath alcohol tests indicate no use, and 2) participant reports no alcohol or drug use since the last test. The escalating schedule has a maximum value of \$570 (complete abstinence). Participants will receive a reloadable prepaid Mastercard (CTpayer, Inc.), and staff will remotely load earned incentives onto the card after each session. The card does not allow teens to withdraw cash. During Weeks 15-26, participants will attend weekly substance testing, and begin a renewed incentive schedule that starts with a \$10 incentive and increases by \$2 per week.

**Working Memory Training.** Usually beginning in Week 2, youth assigned to Treatment A will start WMT and will complete up to 5 WMT sessions per week at the clinic (30-45 min), with the goal of completing at least 25 sessions; this replicates or exceeds the number of WMT sessions from previous studies with adults and adolescents. Youth will be trained using Cogmed-RM (Pearson, Inc), which is a commercially available, program used successfully to train WM in youth samples (e.g., normal, ADHD, low birth weight history). ([Gibson et al., 2011](#); [Holmes et al., 2010](#); [Klingberg et al., 2005](#); [Klingberg et al., 2002](#); [Lohaugen et al., 2011](#)) The PI, Co-I and the RA have obtained administrative and coach training needed to ensure WMT fidelity. Mountain Manor is currently using WMT in a research protocol with the same population targeted for this study.

Each session will include 15 trials from each of 8 of a possible 12 different WM exercises. The program includes a series of verbal and visuospatial WM tasks with appropriately designed graphics and tasks for this age group. Each task involves the temporary storage and manipulation of visuospatial or verbal information, or both. In the adaptive version, an algorithm based on performance automatically adjusts task difficulty and promotes training at a participant's individual WM capacity. An algorithm also rotates exercises so that equal numbers of trials across each of the 12 exercises are completed. The program has built-in motivational features designed to promote effort and interest, including positive feedback, displays of best scores and earnings on an 'energy bar' that activate access to a robo-racing game. We will use additional incentives to reinforce effort and improvement, a technique employed in many rehabilitation programs. Youth will get \$10 on their reloadable card each time they complete a session. Average scores across each session that are equal to or greater than prior sessions earn a second \$5. Youth will also earn a \$20 bonus for either completing 3 or more sessions in a week or completing 1 or more sessions than the week before (minimum of 2 sessions). Participants who meet these criteria throughout the study would earn \$470.

**Intensified Contingency Management (ICM):** After 4 weeks of treatment, response will be assessed. Early responders (those abstinent in Week 4) will continue in their assigned intervention. Non-responders (still using substances in Week 4) will be randomly assigned to either continue with the assigned intervention for weeks 5–14 or to begin the ICM intervention. Those assigned to ICM will discontinue their CM incentive program, and initiate a new 11-week incentive program of higher magnitude during Weeks 5-14. ICM differs from CM in that the magnitude of the incentives will increase by approximately three times the relative magnitude of the initial incentive system. This is consistent with a prior adult study, which yielded a 50% positive response rate with this level of increase. ([Silverman et al., 1999](#)) ICM during this period will have maximum earnings of \$1225 for continuous abstinence across weeks 5-14.

Procedures:

**Initial evaluation, informed consent/assent, treatment assignment.** The youth must attend the intake evaluation, and sign consent/assent forms covering the intake process and trial participation. Participants will be randomly assigned to one of two first-line interventions (CM or CM with active WMT).

Regarding the WMT assignment: Participants will be told, “you will be assigned randomly to either receive 25 sessions of WMT or not.”

Regarding the potential reassignment to ICM, participants will be told: “at week 4, we will assess your treatment response. If you are doing well (not using substances), you will continue with your current treatment plan. If you are still using substances, you will be randomly assigned to either remain in your current treatment or to a treatment with a revised incentive plan. Details of the revised plan will be explained after reassignment.”

Random assignment to the first line intervention (CM or CM/WMT) will occur immediately prior to session 1. Randomizations will be made using minimum-likelihood allocation as done successfully in prior trials to ensure groups are balanced for variables that may correlate highly with outcome assessments. The first randomization will be balanced on 6 measures: 1) abstinence prior to treatment initiation, 2) clinically significant conduct problems at intake, 3) age > 16, 4) gender, 5) race (white vs. other), 6) receiving treatment for opioid use disorder. The second randomization of non-responders will occur in Week 4 and will be balanced on variables 2 through 5.

**Substance monitoring.** Participants provide specimens once-weekly during weeks 1–26. Staff are trained and receive ongoing supervision related to handling questions about urine test results. We will use rapid testing devices that provide qualitative results because of ease of use, low cost, and likely use in dissemination efforts. We will protect from invalid results by using test strips for creatinine levels and four indicators of adulteration. Participants with invalid specimens will be asked to provide another specimen within 4–24 hrs. The criteria for cannabis abstinence will be determined by a negative result on our cannabis rapid testing devices; the cutoff on these devices is 50ng/ml. This is the standard THC level set for establishing abstinence in clinical studies, which reflects the clinical standard for using urine results with abstinence-based contingency management intervention. We, and others, have used these procedures effectively in multiple clinical trials.

Staff contact participants who do not attend the clinic at scheduled times, and when necessary, offer to collect specimens away from the clinic. Outreach collection will occur only with permission from the participants. In prior trials, <3% of specimens were collected away from the clinic. Failure to submit a specimen without making alternative arrangements is treated as testing positive for CM implementation.

### **Statistical Methods.**

The a priori, primary hypothesis of the study was that youth receiving CM \_ WMT would have better substance use outcomes than those receiving CM. When comparing the two Phase 1 intervention conditions, such analyses are no different from those in a “standard” randomized controlled trial. Zero-inflated negative binomial (ZINB) models compared cannabis use (percent days used and WCA) between conditions during the intervention (Atkins, Baldwin, Zheng, Gallop, & Neighbors, 2013). ZINB models were used because both outcomes were zero inflated (\_22% of youth had 0% of days used cannabis and 47% had zero WCA) and somewhat

overdispersed (estimated dispersion parameters: WCA  $\_ .69$ , 95% CI  $[.25, 1.91]$ ; percent days used  $\_ .67$ , 95% CI  $[.36, 1.25]$ ).

Exploratory analyses compared the four treatment strategies embedded in the trial (see Table 1). Analysis of the treatment strategies requires additional statistical considerations (e.g., weighting and the use of robust [sandwich] standard errors), which are described in detail in Nahum-Shani et al. (2012).

In addition, to compare the four strategies simultaneously, duplicate observations for each responder and for each participant who dropped out before the Phase 2 randomization were added to the data set and assigned to multiple strategies based on starting condition and response. For example, responders assigned to stay in STANDARD CM are included in Strategy 1 (all start in STANDARD CM, all stay in STANDARD CM) and Strategy 3 (all start in STANDARD CM, responders stay in STANDARD CM, and nonresponders switch to ENHANCED CM). In these analyses, the “lowest” level of treatment (start in STANDARD CM and stay in STANDARD) was the comparison condition. TLFB models adjusted for baseline TLFB values. A total of 37 of 59 (63%) participants provided TLFB data on at least 25% of the days during treatment. The percentage of nonmissing TLFB data did not differ significantly between treatment arms, age, race, intake use, tobacco use status, or CUD severity (data not shown).

There are no missing WCA data because missing specimens are considered not abstinent. A sensitivity analysis was performed using the number of negative samples, which treated missing specimens as missing. The same pattern of results was observed. All analyses were performed using SAS Version 9.4. All tests were conducted using a two-sided alpha threshold of .05.

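### Does the missing week range for the primary cannabis outcomes call for a change to the plan?

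*Combined protocol and SAP*

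**What the plan says.** The Statistical Methods section states that zero-inflated negative binomial (ZINB) models "compared cannabis use (percent days used and WCA) between conditions during the intervention". It reports that 37 of 59 participants (63%) "provided TLFB data on at least 25% of the days during treatment". Neither phrase carries a week range, and no other section supplies one.

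The design text contains pointers in both directions:

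- **Towards Week 14.** Therapist sessions run through Week 14 (Design, procedures, materials and methods). Under Intensified Contingency Management, non-responders either "continue with the assigned intervention for weeks 5–14 or to begin the ICM intervention".
- **Towards Week 26.** The design section says "Treatment is 26 weeks in duration total". Specimens are collected weekly through Week 26 (Substance monitoring).
- **Undecided.** "Post-treatment assessment will occur at the end of treatment" is undated. "There will be three follow up assessments: 14 weeks, 6 months, and 12 months after intake" names one visit close to each candidate end point.

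The design section also says "Weeks 15-26 involve drug testing only", while the Clinic-delivered CM paragraph describes a restarted incentive schedule in those same weeks, beginning at $10 and rising by $2 a week.

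**The concern.** For a primary comparison, a reader should be able to say which weeks the estimate describes. Here the candidates are 98 and 182 days, and the difference is not cosmetic. In Weeks 15-26 the document describes one testing and incentive schedule for everyone, so a 26-week estimate mixes the effect during active treatment with whatever lasts afterwards.

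Two further points make it look worse. If the outcome was taken over 14 weeks and completeness over 26, the 63% would not describe the outcome it is meant to support. The zero shares used to justify ZINB (about 22% for percent days used, 47% for WCA) also depend on the window. With missing specimens counted as not abstinent, the share with zero WCA can only fall or stay the same as the window lengthens. An open window can also leave room for a choice made after seeing the data.

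**Working it through.** **Inputs.** 37 and 59 participants and the 25% threshold (Statistical Methods); Week 14 and Week 26 as candidate end points (Design section, ICM paragraph, Substance monitoring). WCA is not expanded in the text; I assume it counts weeks of continuous abstinence.

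**The plan's own figure.** 37/59 = 0.627, which rounds to the stated 63%.

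**What the window changes.**

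| | Weeks 1-14 | Weeks 1-26 |
|---|---|---|
| Days (7 × weeks) | 98 | 182 |
| 25% of days | 24.5, so 25 days | 45.5, so 46 days |
| Weekly specimens (maximum WCA) | 14 | 26 |

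A participant with 25 reported days passes on the shorter base (25/98 = 25.5%) and fails on the longer one (25/182 = 13.7%). The document does not say which base gave 37 of 59, so that count cannot be recomputed.

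**Can the effect of the choice be sized?** Only under assumptions. For a difference in mean percent days used, with equal TLFB coverage in every week:

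- An effect confined to Weeks 1-14, averaged over 26 weeks, is multiplied by 14/26 = 0.538, that is 46% smaller.
- An effect that begins in Week 7 and persists is multiplied by (20/26)/(8/14) = 1.346, that is 35% larger.

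The two examples go in opposite directions. They are also differences in means, whereas ZINB estimates a rate ratio for the count part and an odds ratio for the zero part. As an illustration with assumed values, take 40% against 20% of days used in Weeks 1-14 and equal use afterwards. The ratio of means is 0.50 over 14 weeks. Over 26 weeks:

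- later use 40% in both arms: (14×20 + 12×40)/(14×40 + 12×40) = 760/1040 = 0.73;
- later use 60% in both arms: (14×20 + 12×60)/(14×40 + 12×60) = 1000/1280 = 0.78.

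So no single percentage carries over to the planned model.

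**Do the two phrases mean different windows?** Setting the sections side by side:

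- The design section names the arms Treatment A and Treatment B, then calls the same arms first-line interventions.
- The ICM paragraph has responders stay in their assigned intervention; the wording read to participants calls the same thing their current treatment plan.
- Statistical Methods itself speaks of intervention conditions, treatment arms and treatment strategies.

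The two words are used as synonyms. One unstated window named in two ways is the simpler reading. The visit list does not separate the candidates either: 6 months is about Week 26, so listing 14 weeks as a follow-up is no stronger evidence than listing 6 months.

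**Could completeness come mostly from late weeks?** Full TLFB in Weeks 15-26 alone would be 84/182 = 46% of days and would pass the 25% threshold with no data before Week 15. That needs TLFB collection in those weeks. No section gives a TLFB schedule, and the therapist sessions that review substance use are placed in Weeks 1-14.

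**The case for a change.** The strongest case for a change is that the omission touches the primary result and costs a sentence to repair. Even if both phrases mean the same window, the reader still does not know whether it is 98 or 182 days. With only 37 of 59 participants reaching 25% coverage, one is entitled to ask 25% of what. The two descriptions of Weeks 15-26, testing only in one place and testing with incentives in another, leave open whether an intervention was still running.

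The first part stands: the weeks are not stated, and a report of the results is clearer with them. The rest is weaker. A mismatch between outcome and completeness base is possible but rests on a distinction between terms that the document does not keep. A second model on the other window would be a preference rather than a correction, because nothing makes one window right and the other wrong. The wording on Weeks 15-26 is a separate inconsistency of description. The two passages need to be reconciled, but no stated result depends on it.

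**Conclusion.** No change to the plan follows. The week range is missing, but this is a detail that the analyst necessarily supplied in order to fit the models, and both candidate values are sensible. Whichever was used, the same weeks apply to both arms, so the randomised comparison of CM plus WMT with CM is sound. Writing the weeks down would label the estimate without altering it.

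What differs between readings is 98 against 182 days, a threshold of 25 against 46 days, and 14 against 26 specimens. The shift in an estimate cannot be sized from the document; the illustrations above rest on assumed effect patterns and equal TLFB coverage and do not bound it. The 63% reproduces, and nothing indicates that a window was chosen on results.

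The conclusion assumes that one window was applied to both arms and that treatment and intervention are synonyms in Statistical Methods. If completeness had in fact been computed on a different base from the percent-days outcome, the 63% would be a poor description of that outcome's data, but the comparison itself would remain valid.

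### The only check on coding missing specimens as not abstinent is a count of negatives with no stated denominator, which scores missing and positive specimens alike

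*Combined protocol and SAP*

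**What the plan says.** Statistical Methods names two cannabis outcomes for the Phase 1 comparison: "Zero-inflated negative binomial (ZINB) models compared cannabis use (percent days used and WCA) between conditions during the intervention". No offset or exposure term is mentioned for these models. WCA is not defined in the documents.

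For WCA, missing data are removed by rule: "There are no missing WCA data because missing specimens are considered not abstinent". One check on that rule follows: "A sensitivity analysis was performed using the number of negative samples, which treated missing specimens as missing". Its result is given in a single sentence: "The same pattern of results was observed". There is no estimate, interval, model or denominator for the check, and no number of specimens submitted or missing by arm.

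Two other places bear on the point. The Substance monitoring paragraph applies a similar rule to incentive payments: "Failure to submit a specimen without making alternative arrangements is treated as testing positive for CM implementation". Statistical Methods also shows that early dropout occurred, since the exploratory strategy comparison duplicates records "for each participant who dropped out before the Phase 2 randomization". That randomization is placed in the paragraph on initial evaluation and treatment assignment: "The second randomization of non-responders will occur in Week 4".

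**The concern.** A sensitivity analysis of a missing-data rule has to score missing values differently from the main analysis. Here the main analysis treats a missing specimen as a failure. A bare count of negatives does the same, because a missing specimen and a positive one each add nothing to it. The description says missing values were left as missing, but a count has that property only if it is set against the number of specimens submitted.

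This is the only reassurance given for WCA. The design gives some reason to ask whether submission differed by arm: Treatment A youth may come to the clinic up to five times a week for paid training sessions, while the schedule for Treatment B is one therapist session and one drug test a week. If submission did differ, WCA and the count would tend to move the same way, and agreement between them would not show robustness. The self-report (TLFB) outcome does not use this rule and is not affected.

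**Working it through.** The plan gives no figure to reproduce here, so the check is of the scoring itself, followed by an illustration of size.

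**Inputs from the documents.** Weekly specimens (weeks 1–14 for the main treatment phase; testing runs on to week 26); 59 participants; 47% with zero WCA.

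**Assumptions.** WCA is the longest run of consecutive negative weekly specimens; 14 specimens are due; arms of 30 and 29; all submission and dropout rates.

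**Step 1: scoring of single records** (N negative, P positive, M missing)

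| Record | Longest run | Count of N | N / submitted |
|---|---|---|---|
| 6 N, 1 M, 7 N | 7 | 13 | 13/13 = 1.00 |
| 6 N, 1 P, 7 N | 7 | 13 | 13/14 = 0.93 |
| 3 N, then 11 M | 3 | 3 | 3/3 = 1.00 |
| 3 N, then 11 P | 3 | 3 | 3/14 = 0.21 |

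The count relaxes the run-breaking effect of an isolated gap (13 instead of 7). It does not separate M from P in any row; only the last column does.

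**Step 2: all eight-week records.** There are 3^8 = 6,561, of which 6,561 − 2^8 = 6,305 contain at least one M. Changing every M to P alters the longest run in 0 and the count in 0, as must follow from their definitions. It alters N / submitted in 6,051; the other 254 have no negatives. The split into zero and non-zero is identical for run and count in all 6,561. That depends on a one-week minimum for WCA: the split differs in 3,088 records if a run needs two negatives, and in 4,118 if it must start at week 1.

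**Step 3: effect on an arm comparison with equal true abstinence.** If misses are unrelated to use, the expected count is 14 × p × (share submitted), where p is the probability of a negative. The count ratio is therefore the ratio of shares submitted. For dropout after week 3 in a fraction d, mean specimens submitted are 14(1 − d) + 3d: 13.45 at 5%, 12.9 at 10%, 11.8 at 20% and 10.7 at 30%. WCA ratios are simulated with 400,000 youth per arm. A never-abstinent share of 38–43% is set so that 47% have zero WCA, and the remaining youth have a weekly abstinence probability uniform on 0 to 1.

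| Assumed pattern (higher vs lower submission) | WCA | Count | N / submitted |
|---|---|---|---|
| Scattered misses, 90% vs 70% submitted | 0.69 | 0.70/0.90 = 0.78 | 1.00 |
| Scattered misses, 80% vs 70% | 0.84 | 0.70/0.80 = 0.88 | 1.00 |
| Scattered misses, 85% vs 80% | 0.91 | 0.80/0.85 = 0.94 | 1.00 |
| Constant-hazard dropout, averaging 90% vs 70% | 0.82 | 0.70/0.90 = 0.78 | 1.00 |
| Dropout after week 3, 10% vs 30% of youth | 0.86 | 10.7/12.9 = 0.83 | 1.00 |
| Dropout after week 3, 10% vs 20% | 0.93 | 11.8/12.9 = 0.91 | 1.00 |
| Dropout after week 3, 5% vs 10% | 0.96 | 12.9/13.45 = 0.96 | 1.00 |
| Only use weeks skipped, 93% vs 79% submitted | 1.00 | 1.00 | 0.93/0.79 = 1.18 |

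WCA and count move together in every row, whether or not the rule distorts the comparison.

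**Step 4: precision.** In 4,000 simulated trials per scenario the SD of the log ratio for the count is about 0.33 to 0.36. Since exp(1.96 × 0.33) = 1.91, a 95% interval runs from about half to about twice the estimate. A statement that the pattern was unchanged could not reveal a move from 0.78 to 1.00.

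**Step 5: false-positive rates at the 5% level** (a Wilcoxon test for WCA and log-ratio tests for the other two, as stand-ins for ZINB). Scattered misses at 90% vs 70%: 0.077 for WCA, 0.118 for the count and 0.043 per submitted. Week-3 dropout in 10% vs 30%: 0.053, 0.062 and 0.041.

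**The case against.** The strongest reply is that the sentence is only incomplete. A plain count would contradict its second clause, so the analysts may well have used the number submitted as denominator or offset and not said so. That is possible. The remedy is then one sentence, but a reader following the text as it stands would run a check that does not work.

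Second, no harm is shown. All submission rates above are assumed, WCA and its time window are undefined, and the milder scenarios shift the ratios by less than 10%. Staff contacted non-attenders and could collect specimens off site. The one by-arm statement on missing data found no significant difference. All of this stands, although that last statement concerns self-report and does not settle urine submission.

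Third, the incentive rules favor the opposite mechanism. From week 3 only documented abstinence is paid, so a youth who has used gains no abstinence incentive by attending. If only use weeks are skipped, WCA and the count are right and the per-submitted rate errs (1.18 above; 1.33 if 80% vs 50% of positive specimens are submitted). This also stands. It is why the per-submitted analysis should sit beside the present rule as a contrast and not replace it.

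Finally, counting non-submission as failure may be intended, as in the incentive program. The resulting shift is then part of the outcome and not bias. The alternative assumption, however, would still not have been tested by a plain count.

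**Conclusion.** The concern holds. As described, the check cannot do what is claimed for it: a count of negatives without a denominator gives missing and positive specimens the same score, and no other analysis in the documents tests the rule. This follows from arithmetic and does not depend on how WCA is defined. The statement that the zero/non-zero split is the same in both analyses does depend on that definition.

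The likely effect is modest. Under the assumed gaps with misses unrelated to use, the count ratio falls to between 0.78 and 0.96 when the truth is 1.00, and WCA to between 0.69 and 0.96. Whether any such gap occurred cannot be told, because submission and early dropout by arm are not reported. The reported agreement should therefore not be read as evidence that WCA is robust to missing specimens, unless a denominator or offset was in fact used.

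**What to change.** 1. State the denominator or offset if one was used. If none was, analyze negatives out of specimens submitted, with a binomial or beta-binomial model or a count model with log(submitted) as offset.
2. Report specimens due, submitted and negative by arm, and the number in each arm lost before the second randomization.
3. Replace the sentence on the unchanged pattern with the estimate and 95% interval from each analysis.
4. Keep missing as not abstinent for the main analysis and present the two as contrasting assumptions, saying that the per-submitted version misleads if youth skip specimens in weeks of use. A range of assumed abstinence probabilities for missing specimens, varied by arm, is optional.

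The cost is one model and one table on data already held. Intervals may widen somewhat under a beta-binomial model, although in the illustration the SD of the log ratio was 0.33–0.34 per submitted against 0.33–0.36 for the count. Youth with no specimens drop out of the per-submitted model (about 2 of 59 in the constant-hazard dropout illustration). The two analyses may disagree, and that would need to be reported.
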